## 2.2 Secondary Objectives

- Incidence and severity of adverse events (ocular and non-ocular).
- Total number of intravitreal injections required from baseline through weeks 48-57 (week closest to week 52), baseline through week 104 and baseline through week 156.
- Total number of office visits and imaging studies performed from baseline through weeks 24-28 (week closest to week 26), baseline through weeks 48-56 (week closest to week 52), baseline through weeks 72-82 (week closest to week 78), baseline through week 104, baseline through weeks 128-132 (week closest to week 132) and baseline through week 156.
- Percentage of subjects with persistent active exudation on SD-OCT from baseline through weeks 48-57 (week closest to week 52), baseline through week 104 and baseline through week 156.
- Percentage of subjects with persistent leakage on fluorescein angiography from baseline through weeks 24-28, baseline to weeks 48-56, baseline to weeks 72-82, baseline to week 104, baseline to weeks 128- 132 and baseline to week 156.
- CNVM lesion size at baseline, compared to baseline to weeks 24-28, baseline to weeks 48-56, baseline to weeks 72-82, baseline to week 104, baseline to weeks 128-132 and baseline to week 156, as determined by fluorescein angiography.
- Mean change in central foveal thickness by SD-OCT from baseline to weeks 48-57, baseline to week 104 and baseline to week 156.
- Mean change in BCVA by ETDRS letter score from baseline through weeks 24-28, baseline through weeks 48-56, baseline through weeks 72-82, baseline to week 104, baseline through weeks 128-132 and baseline to week 156.

### Endpoint Visits:

Few completed prospective trials have employed a treat and extend protocol. Therefore, there is little data regarding optimal endpoint usage. These endpoints will allow comparison of data from each cohort.

1. **Floating Endpoints** (also known as the Biological Endpoints): Analyses will be performed between weeks 24-28, between weeks 48-57, between weeks 72-82, week 104, between weeks 128-132 and week 156 (range to be determined by timing of last injection). If more than one possible endpoint exists, the time point closest to week 26, week 52, week 78, week 104, week 130 or week 156 will be used. This will be applied to both Cohort A and B, but

likely to be most important for Cohort B. All endpoints are measured 4 weeks following the last injection.

2. **Hard Endpoints:** analyses will be performed at week 52 (day 365± 7 days), week 104 (day 730 ± 7 days) and week 156 (day 1095 ± 7 days).

### **3. STUDY DESIGN**

#### **3.1 DESCRIPTION OF STUDY**

TREX is a phase IIIb, multicenter, randomized, controlled clinical study. Subjects will be randomized 1:2 to “monthly” (control arm) or “treat and extend” protocol (comparator arm) respectively. TREX assess the safety, tolerability and efficacy of intravitreal injections (IVT) of 0.5mg ranibizumab given monthly for up to 100 weeks followed by pro re nata (PRN) treatment for 56 weeks compared to a Treat and Extend protocol for 156 weeks in patients with wet age-related macular degeneration (AMD). Subjects treated in a treat and extend protocol receive 3 consecutive IVT 0.5 mg ranibizumab (visits 2, 4 and 5). Starting at week 8, if a subject has achieved a “dry” macula; signs of active exudation have resolved will begin a Treat and Extend protocol (visits lengthened by 2 week intervals every visit a dry macular is maintained). At the beginning of the 104-week endpoint subjects initially randomized to the TREX cohort will transition to PRN re-treatment when there is no exudative disease activity at the 12-week interval.

#### **3.2 OVERVIEW OF STUDY DESIGN**

This trial will compare the results of 2 cohorts, with different treatment intervals, to assess the safety, tolerability and efficacy of IVT of ranibizumab for the treatment of wet AMD. Specifically, this trial will evaluate the ability to reduce the amount of visits and IVT ranibizumab treatments needed all while maintaining an exudation-free macula. Subjects in both cohorts will be followed for a total of 156 weeks.

**Cohort A** (control arm, monthly, n=20) Subjects will receive monthly treatment of IVT 0.5 mg ranibizumab from Day 0 to week 100. Monthly treatment is defined as every 28 days (±7 days). Dosing should not occur earlier than 21 days after the previous treatment.

#### **Week 104 – Week 156**

Starting at week 104 subjects will be seen monthly and treated with IVT ranibizumab pro re nata (PRN) based on pre-defined re-treatment criteria.

#### **Retreatment criteria for PRN phase**

Re-treatment will be initiated if any of the following criteria are meet:

- Presence of any abnormal intraretinal or subretinal fluid on high resolution SD-OCT.

- Presence of new intraretinal or subretinal hemorrhage related to AMD on examination.
- 10 letter loss from previous visit, related to active wet AMD in the opinion of the treating investigator

**Cohort B** (comparator arm, TREX, n=40) Subjects will receive a minimum of 3 consecutive IVT 0.5 mg ranibizumab (visits 2, 4 and 5). Starting at week 8, if a subject has achieved a “dry” macula; signs of active exudation have resolved by both ophthalmic exam and SD-OCT evaluation they will begin a Treat and Extend protocol.

For a macula to be considered “dry” it must meet both the following criteria:

1. Resolution of intraretinal and subretinal fluid
2. Resolution of all subretinal hemorrhage related to active exudative AMD

Resolution of pigment epithelial detachments (PED) is not required for a macula to be considered “dry”. Small intraretinal cystic areas observed on SD-OCT are acceptable and the corresponding macula can be considered dry. The criteria for these are specific; see reference images (Appendix D) for examples of acceptable intraretinal cystic spaces. When cysts described in Appendix D are present the macula should be considered dry and should be noted on the SD-OCT interpretation. Also, minimal increased retinal thickening on SD-OCT without definitive intraretinal or subretinal exudative fluid can be observed and the corresponding macula will be considered dry.

Once a “dry” macula is achieved the interval between visits is then lengthened by 2-week increments, at every visit the macula is “dry”. IVT ranibizumab will be rendered at every visit, no earlier than 7 days before the target date and no later than 7 days after the target date; the interval between visits is individualized based on each patient’s response to treatment. The interval between injections will not exceed 12 weeks

After a subject is extended beyond 4-weeks and develops recurrent exudative disease activity, the eye is treated and the treatment interval for the next visit is reduced by 2 weeks, compared to the previous treatment interval. The interval between treatments will be reduced by 2-week intervals until a dry macula is again established. Once a dry macula is again achieved, the interval between visits will be extended by 1-week intervals, instead of 2-week intervals.

For example: If recurrent exudative disease activity is detected after an 8-week interval, the eye is treated and the interval for the next visit is reduced to 6 weeks; if the macula is then dry after the 6-week interval, the interval is increased to 7 weeks. If the macula is then dry after the 7-week interval, the interval is increased to 8 weeks, etc.

Once an eye is extended by 1-week intervals, if recurrent exudative disease is detected again, the treatment interval for the next visit is reduced by 1

week, compared to the previous treatment interval, and will continue to be decreased by 1-week intervals until dry or the 4-week interval is reached. Once a dry macula is again established, the most recent interval between treatments is maintained for one additional visit; if the macula remains dry at this time, the interval will then be extended by 1-week increments.

If an eye exhibits recurrent exudative disease three times at a given interval and is unable to extend beyond that interval, the eye will continue treatment at the next shorter interval for 3 consecutive visits. Once the macula has achieved a "dry" status again the treat and extend protocol will re-start, the interval between visits will be lengthened by 1-week increments, at every visit the macula is "dry". If the subject exhibits recurrent exudative disease again the interval will be decreased, the treatment interval for the next visit is reduced by 1 week, compared to the previous treatment interval, and will stay at that interval for 3 consecutive visits before extending by 1 week again.

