Auto Fluorescence	X	X	X	X	X	X	X	X	X	X	X	X	X	X
FP/ FA	X						X							X
CNVM	X						X							X
Measurement														
Study Drug Injection	X	X	X	X	X	X	X	X	X	X	X	X	X	X
Serum and/or Plasma Blood Draw														X

1. Injection administered on a PRN basis, if meets re-treatment criteria 2. Optional

Year 3 T-REX/PRN Treatment Schedule

Week (±7 days)	108	112	116	120	124	128	132	136	140	144	148	152	156
Visit	Visit	Visit	Visit	Visit	Visit	Visit	Visit	Visit	Visit	Visit	Visit	Visit	Visit
Vital Signs	30 X	31 X	32 X	33 X	34 X	35 X	36 X	37 X	38 X	39 X	40 X	41 X	42 X
Interval History (AE & Con Meds)	X	X	X	X	X	X	X	X	X	X	X	X	X
Indirect/Slit Lamp Exam	X	X	X	X	X	X	X	X	X	X	X	X	X
IOP (Pre & Post Injection)	X	X	X	X	X	X	X	X	X	X	X	X	X
Visual Acuity (ETDRS)	X	X	X	X	X	X	X	X	X	X	X	X	X
SD-OCT	X	X	X	X	X	X	X	X	X	X	X	X	X
Auto Fluorescence	X	X	X	X	X	X	X	X	X	X	X	X	X
Fundus Photo/ FA						X							X
CNVN Measurement						X							X
Study Drug Injection	X 												
Serum and/or plasma						X 							X 

1. Injection administered on a PRN basis, if meets re-treatment criteria      2. Optional

T-REX/Treat and Extend Arm/Cohort 2

		Week 12-156					
Week (±7 days)	Screen	Day0	Day7	4	8		
Visit	Visit	1	2	3	4	5	
Sign IFC	X						
Medical/Oph HX	X						
Vital Signs	X	X	X	X	X	X	
Interval History (AE & Con Meds)	X	X	X	X	X	X	
Indirect/Slit Lamp Exam	X	X	X	X	X	X	
IOP (Pre & Post Injection)	X	X	X	X	X	X	
Visual Acuity (ETDRS)	X	X	X	X	X	X	
SD-OCT	X	X	X	X	X	X	
Auto	X	X	X	X	X	X	
Fluorescence FP/FA	X						
CNVM Measurement	X						
Study Drug Injection 		X			X	X	
Plasma and/or Serum Sample 							

- Cohort 2 will receive 3 mandatory 0.5mg ranibizumab injections (Day 0, week 4, & week 8)
- Interval will remain at 4 weeks until there are no signs of exudative disease on SD-OCT or clinical examination
- Once a dry macula is achieved meaning there are no signs of exudative disease on SD-OCT or clinical examination the subject will start the Treat and Extend protocol, interval between injections is increased by 2-week intervals, starting at visit 6.
  - o Treatment Interval will not exceed > 12 weeks.
- If recurrent exudative disease is detected at any visit, after extension has been met, the interval between injections will decrease by 2 weeks (compared to the previous interval) until a "dry" macula is again established or subject is back at the 4-week interval.

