  - o Once a dry macula is again achieved the interval between visits will extend by 1-week intervals.
  - o If subject again shows signs of recurrent exudative disease, interval will be by 1 week until dry or subject is back at 4 week interval
  - o Once macula is again dry, treatment interval remains at the same interval for 1 more treatment, after which the treatment interval will be increased by 1-week intervals if the macula remains dry.
    - If patient shows signs of exudative disease 3 times at a certain interval, interval will be decreased by 1 week intervals until the macula is dry AND then remain at this reduced interval for 3 sessions then re-start the treat and extend protocol (meaning extend by 2 week intervals at every visit a dry macula is achieved.
- **Endpoint Measurements:** Additional visits will be scheduled 4 weeks post injection within the "quarterly report" windows defined below. In the event that two possible additional sessions (4 weeks post injection) can be scheduled within a quarterly window, schedule the session which falls closest to the 26 week, 52 week, 78 week, 104 week, 128 week and 156 week marks; if the two sessions are equally spaced around an endpoint, use the earlier. Refer to protocol for visit windows for floating endpoint visits. BCVA, SD-OCT, AF and FA/FP will be performed at the floating endpoint visits.
  - Hard-endpoints will be additional visits at week 52, week 104, and week 156 (± 7 days). BCVA, AF and SD-OCT will be performed at the hard end point visits.

1. Performed at week 104, week 128 & week 156 2. Study drug injection not administered at week 156 3. Optional

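### After three recurrences at one interval, section 3.2 re-extends treat-and-extend eyes by 1 week per dry visit and Appendix A by 2 weeks, and no text says which governs

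*Combined protocol and SAP*

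**What the plan says.** Two places give the Cohort B extension rule: section 3.2 (Overview of Study Design, Cohort B) and the notes under the Treat and Extend Arm/Cohort 2 schedule in Appendix A. Both cover an eye that has shown exudation three times at one interval.

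- **The hold.** Section 3.2: "the eye will continue treatment at the next shorter interval for 3 consecutive visits". Appendix A: "interval will be decreased by 1 week intervals until the macula is dry AND then remain at this reduced interval for 3 sessions".
- **Re-extension after the hold.** Section 3.2: "the treat and extend protocol will re-start, the interval between visits will be lengthened by 1-week increments". Appendix A: "re-start the treat and extend protocol (meaning extend by 2 week intervals at every visit a dry macula is achieved".
- **A further recurrence after the re-start.** Section 3.2 shortens the interval by 1 week, and the eye "will stay at that interval for 3 consecutive visits before extending by 1 week again". Appendix A does not repeat this rule.

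Appendix A has two general recurrence rules. The first is "If recurrent exudative disease is detected at any visit, after extension has been met, the interval between injections will decrease by 2 weeks", after which "Once a dry macula is again achieved the interval between visits will extend by 1-week intervals". The second, for a repeat recurrence, is a 1-week reduction until dry, after which the "treatment interval remains at the same interval for 1 more treatment" before extension resumes.

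Section 4.5.1 points to Appendix A only as an overview of procedures. Appendix A points back to the protocol only for the floating-endpoint windows. Neither sets an order of precedence.

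**The concern.** The extension rule is the experimental intervention. A site working from section 3.2 and a site working from the Appendix A schedule would both comply, yet they would give the same eye different target intervals.

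The Appendix A step also runs against the logic of the rest of the rule. After one recurrence both texts drop to 1-week steps. After three failures at one interval, Appendix A goes back to 2-week steps, which is less cautious for an eye that has proved harder to control.

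The stake is larger in year 3. Under section 3.2, an eye not yet at 12 weeks continues treat and extend after week 104, and a dry macula at 12 weeks switches it at once to monthly visits with as-needed (PRN) treatment. For an eye that stays dry, the step size therefore sets the date on which scheduled injections stop. Injections through week 156 are a secondary outcome (section 3.4.2).

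**Working it through.** The plan gives no figure to reproduce, so the check steps both rules through the visit calendar.

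**Inputs from the documents.** Injections at weeks 0, 4 and 8; 2-week extension when dry; 2-week reduction at the first recurrence, then 1-week extension; 1-week reduction at a repeat recurrence with one extra visit at that interval; three-visit hold after three recurrences at one interval; 12-week cap; no injection at week 156.

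**Assumptions, not in the documents.** The eye is first dry at week 8, 12 or 16. Until the hold it is dry at intervals up to T weeks and wet beyond, with T from 4 to 11, so the failed interval is T + 1 and the hold is at T.

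**Example, T = 7, first dry at week 8 (w = wet).** Visits fall at weeks 0, 4, 8, 14, 22w, 28, 35, 43w, 50, 57, 65w, 72, 79, 86. That is three failures at 8 weeks, then three visits at 7 weeks. The next visit is at 86 + 8 = 94 under section 3.2 or 86 + 9 = 95 under Appendix A. The 8-week interval that failed three times is retried by section 3.2 and skipped by Appendix A. An eye first dry two weeks below the failed interval would instead go straight back to it under Appendix A.

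**Case 1: the eye stays dry after the hold.** PRN start = week the hold ends + sum of the remaining intervals up to 12, or week 104 if that is later. For T = 7:

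- Section 3.2: 86 + (8 + 9 + 10 + 11 + 12) = 86 + 50 = 136.
- Appendix A: 86 + (9 + 11 + 12) = 86 + 32 = 118.
- Treat-and-extend injections: 14 up to week 86, then 4 more (94, 103, 113, 124) or 2 more (95, 106), giving 18 v 16.

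First dry at week 8:

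| T | Hold ends | Next target, 3.2 v App. A | Weeks to complete 12-week interval | PRN start, 3.2 v App. A |
|---|---|---|---|---|
| 4 | 61 | 66 v 67 | 68 v 36 | 129 v 104 |
| 5 | 60 | 66 v 67 | 63 v 39 | 123 v 104 |
| 6 | 91 | 98 v 99 | 57 v 30 | 148 v 121 |
| 7 | 86 | 94 v 95 | 50 v 32 | 136 v 118 |
| 8 | 123 | 132 v 133 | 42 v 22 | not by 156 v 145 |
| 9 | 114 | 124 v 125 | 33 v 23 | 147 v 137 |

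T = 10 does not reach the step by week 156. For T = 11 the cap makes both rules give 12. Over first-dry weeks 8, 12 and 16, where both start dates fall by week 156, the gap runs from 10 weeks (T = 9) to 32 weeks (T = 4, first dry at week 16: 137 v 105; injections 24 v 20). Appendix A gives 0 to 1 fewer injections by week 103 and 1 to 4 fewer by week 155, not counting PRN injections. If the hold is read as three visits after the first dry one, the last range is 0 to 4.

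**Case 2: the eye keeps failing above T.** The step is reached before week 104 for T = 4 to 7 and by week 156 for T = 4 to 9. Injections do not differ by week 52 for any T. Later results depend on how Appendix A is read after a further recurrence. By week 155 it gives 0 to 2 fewer injections and 0 to 3 more wet visits. If the 2-week step is retaken after every recurrence, these rise to as many as 4 fewer and 4 more.

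Example of the upper end, T = 4, first dry at week 8, with 15 injections up to week 61:

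- Section 3.2 repeats a 17-week cycle (5 + 4 + 4 + 4) and adds 22 injections by week 155, total 37, with 6 wet visits (66, 83, 100, 117, 134, 151).
- Appendix A, with a 2-week reduction and the 2-week step retaken, repeats a 10-week cycle (6 + 4) and adds 18, total 33, with 9 wet visits (67, 77, and so on to 147).

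**Visit window.** Section 3.2 allows 7 days either side of the target. The first targets are 1 week apart, so the window can hide that gap. If that visit is dry, the next target intervals for T = 7 are 9 v 11 weeks. From a visit at week X the windows are X + 8 to X + 10 and X + 10 to X + 12, which meet on one day only.

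**The case against.** The conflict itself is not in dispute; the objections concern its weight.

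- **The largest figures need an unlikely eye.** The 10-to-32-week gap requires an eye that failed three times at one interval to stay dry at every longer one. The documents give no frequency for this. If the eye goes on as before, the difference is a few injections at most. This stands.
- **The case 1 injection counts are not the outcome measure.** Section 3.4.2 counts all injections. PRN starts earlier under Appendix A, with monthly visits and retreatment for any abnormal fluid, so the sign of the net difference through week 156 is unknown. This stands.
- **Appendix A's repeat-recurrence rule may be meant to cover later recurrences too.** That is a fair reading, and leaving out a rule stated in the body does not contradict it. This part of the point is secondary.
- **The 12-week cap does not remove every difference at the top.** An eye that fails at 12 weeks and is first dry at 10 would go to 11 under section 3.2 and 12 under Appendix A. This widens the scope slightly.
- **The sponsor's intent is not documented.** Choosing section 3.2 is an inference, and the sponsor should confirm it.

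None of this reconciles the two step sizes.

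**Conclusion.** The concern holds. Two current passages give different dosing steps for the same event in the experimental arm, and nothing ranks them. Section 3.2 is the likelier intent: its 1-week step matches the step both texts use after a single recurrence, and it alone spells out what follows a recurrence after the re-start.

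The expected effect on group results through week 104 is small: nothing by week 52, and usually 0 to 1 injection per affected eye by week 103. It can grow in weeks 104 to 156, where the step size can move the switch to PRN by months for an eye that stays dry. No effect on visual acuity, the primary outcome, has been shown.

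These sizes rest on the assumed dry threshold T and first-dry week. Only Cohort B eyes (n = 40) with three recurrences at one interval are exposed, and the documents do not say how many to expect. The point should be fixed because the rule is wrong as written and the correction is cheap.

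**What to change.** Once the sponsor has confirmed that the 1-week step is intended:

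1. Change the Appendix A line to 1-week increments after the hold, matching section 3.2.
2. Copy into Appendix A the section 3.2 rule for a recurrence after the re-start: shorten by 1 week, hold for 3 visits, then extend by 1 week.
3. Use one wording in both places for the reduction before the hold: shorten by 1 week until dry, then hold for 3 visits.
4. Notify sites, and flag in the data any eye already re-extended by 2 weeks.

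The cost is one changed line, one copied rule, one shared wording and a clarification letter to about 4 sites. Apart from the flag, no new data are needed.

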#### **Evidence of recurrent exudative activity**

Clinical evidence of recurrent exudative disease activity requiring reducing the interval between treatments includes any of the following:

1. Evidence of subretinal or intraretinal fluid on SD-OCT which is *not* classified as small intraretinal cystic areas unrelated to active exudative AMD (Appendix D) or minimal increased retinal thickening by SD-OCT without definitive intraretinal or subretinal fluid
2. New macular hemorrhage related to active exudative AMD.
3. ETDRS VA loss of 5 letters from the previous measurement due to neovascular AMD disease process with corresponding SD-OCT evidence of fluid in the macula.
4. Increase in CRT of 50 microns due to active exudative AMD.

The isolated presence of a PED, or enlargement of a PED, does not constitute evidence of exudative disease activity.

If an eye has an ETDRS VA decrease of  $\geq 4$  lines (20 letters) or a subretinal macular hemorrhage of 1DD or larger, at any point during the trial, the subject will subsequently be treated with ranibizumab every 4 weeks.

#### **Week 104 – Week 156**

Starting at Week 104 subjects who have achieved a "dry" macula, at the 12 week interval will be seen monthly and treated pro re nata (PRN) based on pre-defined re-treatment criteria. Study visits should be scheduled to occur every 28 ( $\pm 7$ ) days relative to the date of week 104 visit.

### **Retreatment criteria for PRN phase**

Re-treatment will be initiated if any of the following criteria are met:

- Presence of any abnormal intraretinal or subretinal fluid on high resolution SD-OCT.
- Presence of new intraretinal or subretinal hemorrhage related to AMD on examination.
- 10 letter loss from previous visit, related to active wet AMD in the opinion of the treating investigator

Starting at Week 104, subjects who have NOT achieved extension to the 12-week treatment interval will continue with the treat and extend protocol. At any time during weeks 104 to 156 if a subject achieves a "dry" macula, at the 12-week interval, they will immediately begin monthly PRN treatment based on pre-defined re-treatment criteria. Study visits should be scheduled to occur every 28 ( $\pm 7$ ) days, relative to the date the 12-week interval is achieved. Subjects will not be treated at the visit they achieve the 12 week interval (this is the date PRN treatment will begin).

